14.6 Overdose

Overdose is defined as an accidental or intentional/infusion or excessive dose of a product.

14.7 Collection of Adverse Events/Serious or Unexpected

Any adverse event occurring prior to signing the ICF and prior to 1st dose of study drug should be considered medical history or a pre-existing condition and will be collected on the Medical History CRF.

SAEs will be assessed and recorded beginning with study drug administration until 30 days after discontinuation of study drug.

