17. For the Prospective Group: All vasopressors must be stopped prior to treatment with terlipressin. Use of vasopressors (eg, norepinephrine, epinephrine or vasopressin dopamine or other vasopressors) of ≥ 3 consecutive days within the prior 14-day screening period are excluded. Patients receiving a vasopressor other than midodrine within 24 hours of qualifying SCr are excluded, i.e, a 24-h washout is required prior to enrollment.
Note: Patients receiving midodrine and octreotide may be enrolled. Midodrine and octreotide treatment must be stopped prior to enrollment.
18. Known allergy or sensitivity to terlipressin.

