13.2 Secondary Efficacy Variables

- Improvement of renal function (SCr) from Day 1 through end of treatment, repeated measure analysis as compared to the Retrospective Control Group.
- For the Prospective Terlipressin Group alone and also in comparison to the Retrospective Control Group:
 - Incidence of dialysis by Day 30 and Day 90 of follow up.
 - Survival by Day 30 and Day 90 follow up.
 - Transplant by Day 30 and Day 90 follow up.
 - Serum creatinine at Day 30 and Day 90 follow up
 - Serum creatinine and incidence of dialysis at Day 30, Day 90, Day 180, and Day 365 after liver transplantation
 - Incidence of kidney transplant within one year after liver transplant
 - Descriptive analysis of number simultaneous liver kidney transplants and episodes of graft rejection at Day 90 and Day 365 after liver transplant

14 Serious Adverse Events

Only Serious Adverse Events will be collected for this study for the prospective group only. Safety review and assessments will be made only for the Prospective Terlipressin Group from time of first dose through 30 days after end of treatment. SAEs are collected from the start of study drug until 30 days after study drug was discontinued. Non-serious Adverse Events are not required to be collected for this study.

The investigator will record the nature, causality, severity, treatment, and outcome of the SAE, and will determine whether there is a “reasonable probability” that the study drug treatment caused the event.

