15.6 Safety Population

The safety population is defined as all subjects who received at least 1 dose of study drug.

16 Direct Access, Data Handling, and Record Keeping

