18.3 Informed Consent

All subjects will have a signed document allowing the use of their medical data. For the Prospective Terlipressin Group, written informed consent will be obtained from all subjects (or their guardian or legal representative) before any study-related procedures (including any pre-treatment study-specific procedures) are performed. The investigator(s) has both ethical and legal responsibility to ensure that each subject being considered for inclusion in this study is given a full explanation of the protocol. This shall be documented on a written informed consent form, which shall be approved by the same IRB responsible for approval of this protocol. Each informed consent form shall include the elements required by regulatory regulations in 21 Code of Federal Regulations (CFR) Part 50 and ICH Guidance E6, Section 4.8. The investigator agrees to obtain approval from the sponsor of any written informed consent form used in the study, preferably prior to submission to the IRB.

Once the appropriate essential information has been provided to the subject and fully explained by the investigators (or a qualified designee) and it is felt that the subject understands the implications of participating, the subject and the investigator (or designee) shall sign the IRB-approved written informed consent form. The subject shall be given a copy of the signed informed consent form, and the original shall be kept in the site's regulatory file. A second copy may be filed in the subject's medical record, if allowed by the institution.

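### Serious events between consent and first dose fall outside the SAE window, and section 14.7 does not clearly assign them to any record

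*Combined protocol and SAP*

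**What the plan says.** Section 14 fixes the recording window: "SAEs are collected from the start of study drug until 30 days after study drug was discontinued". Section 14.7 repeats it: "SAEs will be assessed and recorded beginning with study drug administration until 30 days after discontinuation of study drug". For what comes earlier, section 14.7 says: "Any adverse event occurring prior to signing the ICF and prior to 1st dose of study drug should be considered medical history", and that such an event "will be collected on the Medical History CRF".

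Exclusion 17 in section 7.3, for the prospective group, says: "All vasopressors must be stopped prior to treatment with terlipressin". It adds a 24-hour washout for vasopressors other than midodrine, and a note: "Midodrine and octreotide treatment must be stopped prior to enrollment". No minimum time off midodrine/octreotide is given.

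Section 18.3 requires written consent before study-related procedures, "including any pre-treatment study-specific procedures".

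Table 1 tracks RRT, TIPS, transplant and death through the active study period and follow-up. Section 10.3 starts the active study period when study treatment starts. Section 15.6 defines the safety population as "all subjects who received at least 1 dose of study drug".

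**The concern.** The protocol makes entry depend on stopping certain drugs. When this is done so that a consented patient can qualify, any harm from it is a consequence of taking part in the trial, and it can occur before the first dose. The SAE window opens only at that dose.

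The situation is foreseen. The note to exclusion 17 expressly allows patients on midodrine/octreotide to be enrolled once treatment is stopped. Section 3.5.2 describes the combination as long used off-label in the United States, and section 3.5.1 says midodrine raises blood pressure. Harm from withdrawal is therefore plausible, although the documents report none.

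At stake is safety oversight. Non-serious events are not required (section 14), so SAE capture carries most of the safety assessment. A serious event in the interval would not trigger the 24-hour report to the sponsor. The most severe cases are also the likeliest to be lost: shock (exclusion 5) and current or anticipated RRT (exclusion 14) bar dosing, so whether a subject enters the safety record can depend on how that subject fared after consent.

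**Working it through.** No arithmetic applies, because the plan states no rate or count for this interval. The check sets the sections side by side.

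**Step 1: order of events.** Section 18.3 puts consent before any study-specific step. A stop made in order to satisfy exclusion 17 is such a step, and it must precede the first dose. The order is consent, then stop, then first dose.

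**Step 2: what section 14.7 covers.** The sentence joins two conditions, before the ICF and before the first dose.
- Read as 'and': consent always precedes dosing, so the second condition adds nothing. Only events before consent are medical history. The interval from consent to first dose belongs neither to medical history nor to SAEs.
- Read as 'or': everything before the first dose is medical history. An event that began after consent, possibly because of a trial requirement, is then filed as pre-existing.

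Under neither reading is the event an SAE.

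**Step 3: where a serious withdrawal effect goes, by onset.**

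| Onset | Record under the current text |
|---|---|
| Before consent | Medical History CRF |
| After consent, before first dose | Not an SAE; medical history only on the loose reading of 14.7 |
| First dose to 30 days after discontinuation | SAE, reported whatever its cause (14.12); worsening of a baseline condition may also qualify (14.9) |

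**Step 4: the subject who is never dosed.** Three other places might hold such a case.
- Table 1 with section 10.3: RRT and death are followed from the start of treatment, so the subject is not covered.
- Section 15.6: at least one dose is required, so the subject is not in the safety population.
- Section 15.5: completion status and reasons for stopping are summarised, but subjects who consented and were not dosed are not asked for.

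**The case against.** The strongest case on the other side is that the gap may be narrow.

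- Midodrine/octreotide needs no minimum off-drug time, so its interval could be close to nil.
- The 24-hour rule is written as an eligibility status tied to the qualifying SCr. Many patients may meet it through ordinary care before consent, and their earlier events are properly medical history.
- Exclusion 17 also bars vasopressor use on 3 or more consecutive days in the prior 14 days, which limits the group further.
- A safety population of dosed subjects suits a study of terlipressin infusion.

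All of this stands. It limits how often the gap would matter, but it does not supply a record for an event that falls in it.

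A reader might infer that harm from the required withdrawal is never counted. The documents do not support that. From the first dose, section 14.12 requires every SAE to be reported, related or not, and section 14.9 allows worsening of a baseline condition to count.

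A reader might also infer that the sponsor cannot learn of such an event. Section 18.1 requires prompt IRB reporting of unanticipated problems that put subjects at risk, sets no first-dose limit, and has IRB correspondence shared with the sponsor. Section 14.8 asks for serious laboratory abnormalities to be reported and states no start date. These routes are narrower than SAE reporting and put nothing in the SAE tables, so they are only a partial backstop.

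**Conclusion.** The point holds in limited form. Serious events with onset between consent and first dose are outside the SAE window, section 14.7 does not clearly place them anywhere, and a subject who deteriorates then and is never dosed also drops out of RRT and mortality tracking and the safety population. For withdrawal harm, this rests on one premise: at least some subjects stop a drug after consent in order to qualify. The protocol allows this but does not say how many would.

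The size cannot be estimated. A reader might try subjects × days × daily SAE hazard. With assumed inputs this gives 10 × 1 × 0.02 = 0.2 to 25 × 2 × 0.05 = 2.5 events. None of those inputs is in the documents, and an all-cause hazard in very ill patients would not measure withdrawal harm, so the range should not be used as a finding.

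Nor do the documents show that the safety results for terlipressin itself would look too favourable. Those results concern dosed subjects, and safety is assessed only in the prospective group, so no between-group safety comparison is distorted. The primary SCr analysis is not affected. The reason to act is oversight: the stated rule can miss harm that the trial's own entry requirement causes, and the repair is small.

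**What to change.** - **Sections 14 and 14.7:** record and report SAEs from signing of the ICF, or at least those attributable to protocol-required steps. Limit medical history to events before the ICF, which removes the ambiguous 'and'. Bring the SAE row of Table 1 into line.
- **Section 15.4:** list SAEs between consent and first dose separately from those after first dose, so that the on-treatment results are unchanged.
- **Section 15.5:** account for every consented subject who was not dosed, with the reason (death, RRT, shock, transplant, other).
- **Section 15.6:** keep the safety population as dosed subjects.

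No change to the withdrawal or washout rules is proposed. The cost is a few sentences, one listing, one row in the disposition table and a few extra SAE forms, using existing staff and forms.

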14.8 Laboratory Abnormalities

The investigator will review clinical laboratory test results in a timely fashion. Laboratory abnormalities deemed clinically significant and serious should be reported to the sponsor as appropriate.

14.9 Hospitalizations

Planned hospital admissions and/or planned surgical operations for an illness or disease, which existed before the subject was randomized are not to be considered SAEs (e.g., re-hospitalization for liver transplantation). However, a baseline condition which deteriorates during the clinical study may be considered an SAE.

Following the initial hospital discharge, all re-hospitalizations within 30 days post end of treatment (except for planned hospital admissions or procedures as described above) are to be recorded as a SAE.

14.10 Complications of the Disease

Complications frequently associated with HRS - AKI are expected to occur, but should be recorded as a SAE, as applicable, e.g., EVH, hepatic encephalopathy, sepsis, pneumonia, urinary tract infection.

Since HRS - AKI is the indication under investigation, worsening or aggravation of HRS - AKI during the active treatment period (including non-response) will NOT be recorded as a SAE unless HRS – AKI is the cause of death or results in a subsequent re-hospitalization due to suspected recurrence.

14.11 Pregnancy

Pregnancy occurring in a subject is NOT considered an SAE. However, the investigator must collect pregnancy information for subject and/or subject's partner if the fetus was exposed to the study drug.

14.12 Reporting Serious or Unexpected Adverse Reactions or Adverse Events

Site Reporting to Sponsor

**Collaborative Research Study, Version 4: 06/29/21
To Treat HRS-AKI Patients with Continuous Terlipressin Infusion**

Investigators must report all SAEs to the sponsor (and applicable IRB) whether or not the events are study drug-related or expected.

All SAEs must be reported on a SAE form and faxed/scanned to International HealthCare (IHC) within **24 hours** of an investigator becoming aware of the event:

IHC Safety Review Officer
Email: [contact]

The initial SAE form does not need to be signed by the investigator; however, a signed SAE form is required for final SAE reporting. The initial scan by the investigator will include (whenever possible) a detailed description of the event including start and stop dates, causality assessment by the investigator, and supported as needed with written copies of medical records, autopsy reports, and other appropriate documents. Follow-up information (including information requested by the sponsor) should be reported by fax/scan within 24 hours of availability. The investigator is expected to make every effort to collect follow up information for each SAE in a timely fashion after the initial reporting of the SAE.

If there are any specific questions regarding a SAE classification, the investigator should contact the lead sponsor Principal Investigator for this study.

If there are any specific questions regarding the completion of the SAE form, please contact your site monitor.

Site Reporting to Institutional Review Board/Independent Ethics Committee

The investigator must notify the local IRB which approved the trial of the event in accordance with applicable guidelines.

Sponsor Reporting to Regulatory Authorities and Investigators

All reportable SAEs, including narrative safety reports of overall findings or data from aggregate analyses, will be reported to the applicable regulatory authorities by the sponsor or designee in accordance with the local regulations as described in the safety review plan for this study. The reporting of SAEs will be conducted in accordance with ICH E2A (Clinical Safety Data Management: Definitions and Standards for expedited reporting) and regulatory guidelines.

In addition, study endpoints described in Section 5.1 of the protocol that are serious adverse events will only be reported in the final clinical study report unless the event was unusual,

unexpected, and there is evidence suggesting a causal relationship between the study drug and the event (e.g., death from anaphylaxis).

The sponsor will notify all participating Investigators of safety reports, in a blinded fashion, of potential serious risks as described in the safety review plan for this study.

15 Statistical Plan

Baseline characteristics, such as patient demographics, disease etiology, disease severity and factors present at time of listing for liver transplantation, will be compared between the terlipressin treatment group and the retrospective control group. Categorical variables will be presented as proportions and percentages and compared using chi-squared or Fisher's exact testing. Continuous variables will be presented as means and standard deviations or medians and interquartile ranges. Depending on the distribution of the variable, the Student's t-test or Wilcoxon rank sum will be used for comparison.

15.1 Primary Analysis

The primary analysis will utilize mixed effects regression modeling to estimate changes in serum creatinine (SCr) over the study period, accounting for baseline SCr and the correlation structure between the repeated measures. All potential confounders will be added to the model and sequentially removed if they do not confound the association between receipt of terlipressin and improvement in Scr. Those confounders resulting in a $\geq 10\%$ change in the coefficient for the association between terlipressin and improvement in SCr will be retained in the final model. For all generated models, Aikaike Information Criteria (AIC) scores will be calculated and compared. The model with the smallest absolute AIC value will be accepted as the most parsimonious and will be used as the primary model for the explanation of study results. As has been undertaken in other terlipressin studies in HRS, a least-squares means analysis will be conducted using a repeated-measures analysis of variance. The results from this approach to the statistical analysis can then be directly compared to prior study results.

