15.3 Sample Size Considerations

A formal sample size calculation is not applicable for the proposed study. However, at least 50 subjects across more than 5-10 institutions may receive terlipressin treatment during the course of the intervention portion of the study. For the comparison of the terlipressin treatment group and retrospective controls, we expect to have 50 subjects in the intervention group and 150 subjects, assembled from the study sites, in the control group. Assuming a type 1 error of 0.05 and power of 80%, we expect to be able to detect a range of differences in serum creatinine (SCr) depending on the standard deviation of the change (primary endpoint) expected for the groups (see below). Based on results from the REVERSE trial, a change in SCr of as small as 0.05 mg/dL would be able to be detected if the standard deviation for the change approximated 0.10 mg/dL and a pre-specified sample size of 200 subjects, 50 of whom are in the intervention arm, is used for the calculation.

	Δ SCr mg/dL				
Detectable Difference	0.46	0.34	0.23	0.11	0.05
Standard Deviation	1.00	0.75	0.50	0.20	0.10

Given the relatively small number of subjects proposed for inclusion in this terlipressin study, we will likely be underpowered to detect a difference in the other secondary outcomes being explored.

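### The 10% confounder-removal rule in Section 15.1 names no reference model, no cumulative limit and no precedence over AIC, so a substantial part of the confounding can return to the terlipressin comparison

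*Combined protocol and SAP*

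**What the plan says.** Section 15.1 (Primary Analysis) fits a mixed effects model to serum creatinine (SCr), "accounting for baseline SCr and the correlation structure between the repeated measures". For the other covariates it gives a backward procedure: "All potential confounders will be added to the model and sequentially removed if they do not confound the association". The retention criterion follows: "Those confounders resulting in a $\geq 10\%$ change in the coefficient for the association" between terlipressin and SCr improvement stay in what the section calls the final model. A second selection step comes next, with AIC computed for every model generated: "The model with the smallest absolute AIC value will be accepted as the most parsimonious and will be used as the primary model".

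The candidate confounders are not listed. The nearest thing is the opening paragraph of Section 15, which names classes of baseline variables, "such as patient demographics, disease etiology, disease severity and factors present at time of listing for liver transplantation", that "will be compared between the terlipressin treatment group and the retrospective control group". Section 15.3 gives the planned sizes: "we expect to have 50 subjects in the intervention group and 150 subjects, assembled from the study sites, in the control group".

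Three things are left open: the model against which the 10% is measured, any limit on the total change across removals, and which of the two selection rules prevails.

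**The concern.** The comparison sets prospectively treated patients against historical controls going back to January 2015. It is not randomised, and the documents specify no matching or weighting. Covariate adjustment in the model therefore carries most of the burden of making the groups comparable, and a rule that discards covariates bears directly on validity.

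A 10% threshold controls each step, not the sum of the steps. If the yardstick moves with every removal, or each confounder is screened alone, many small confounders can pass individually while their combined effect is large.

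The threshold is also relative. Ten percent of a coefficient of −0.60 mg/dL is 0.06 mg/dL; ten percent of −0.10 is 0.01. The larger the apparent drug effect, the more confounding each step may discard. Intervals from the selected model take no account of the selection.

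**Working it through.** **Plan's own figure.** Section 15.3 gives no figure for residual confounding, but its detectable difference supplies an effect size. With 50 and 150 patients, two-sided alpha 0.05 and 80% power, the formula is SD × (1.960 + 0.842) × √(1/50 + 1/150). At SD 1.00 this is 2.802 × 0.163 = 0.458, which matches the stated 0.46. (The table's 0.11 at SD 0.20 comes out at 0.09; that is a separate matter.)

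**Arithmetic without sampling error.** Assume five independent confounders, each worth 8% of the fully adjusted coefficient, which is set to 1.00.

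- Inflating, judged against the preceding model: 1.00 → 1.08 → 1.16 → 1.24 → 1.32 → 1.40. The steps are 8.0%, 7.4%, 6.9%, 6.5% and 6.1%. All five go and all the confounding returns.
- Inflating, judged against the full model: 1.08 passes and 1.16 (16%) does not. The process stops at 1.08, so one fifth returns.
- Shrinking, judged against the preceding model: 1.00 → 0.92 → 0.84 → 0.76. The next step is 0.08/0.76 = 10.5%, so it stops with 60% returned.
- At 12% each, every confounder is kept and nothing returns.

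**Simulation at the planned size.** The sizes (50 vs 150) come from Section 15.3. Everything else is assumed: eight confounders that favour terlipressin, each imbalanced by 0.25 SD; residual SD 0.7 mg/dL; true effect −0.60; patient-level linear regression standing in for the mixed model; 600 replicates. Each confounder is worth 0.10 mg/dL per SD if independent and 0.08 if correlated at 0.3. The unadjusted bias is 8 × 0.25 × 0.10 = 0.20 (estimate −0.80) or 8 × 0.25 × 0.08 = 0.16 (estimate −0.76). One independent confounder contributes 0.25 × 0.10 = 0.025, or 4.2% of 0.60.

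| Rule | Independent: estimate (95% CI coverage) | Share of bias returned | Correlated 0.3: estimate (coverage) | Share returned |
|---|---|---|---|---|
| Full model, no removal | −0.60 (about 95%) | 0 | – | – |
| 10% vs preceding model | −0.77 (about 65%) | 0.17/0.20 = 85% | −0.64 (about 92%) | 0.04/0.16 = 25% |
| Each screened singly | −0.76 (68%) | 0.16/0.20 = 80% | −0.75 (about 75%) | 0.15/0.16 = 94% |
| 10% vs full model | −0.65 (92%) | 0.05/0.20 = 25% | – | – |
| Lowest AIC among models generated | −0.61 (about 93%) | 0.01/0.20 = 5% | – | – |

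Repeat runs of the preceding-model rule with independent confounders gave −0.75 to −0.77 and coverage of 63% to 70%, with about 0.5 of the eight confounders kept. The AIC row takes the lowest AIC, which equals the smallest absolute value when all values are positive.

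**Other settings, preceding-model rule, same independent confounders.**

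- True effect −0.40: −0.51, coverage about 75%.
- The plan's 0.46 at SD 1.0, entered as −0.46: −0.56, coverage 82%, against −0.46 and 96% for the full model.
- No true effect: nearly harmless, coverage 94%.
- Direction of confounding reversed, true −0.60: −0.47, so the benefit is understated.

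**Second set of assumptions.** Here the true effect is 0.46, SD 1.0, with 3 to 8 confounders worth 5–8% each and an imbalance of 0.3 SD. The shares of confounding returned were:

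- preceding-model rule: 26–50% (independent), 8–31% (correlated 0.3);
- full-model reference: 5–30%;
- single screening: 34–49% (independent), 52–73% (correlated 0.3);
- lowest AIC: 0–22%.

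**The case against.** The strongest reply is that Section 15.1 does not end with the 10% rule. If AIC chooses among all generated models, covariates that predict SCr are mostly kept and the bias nearly disappears. That is right as far as it goes. However, the section calls the survivors of the 10% rule the final model and the AIC choice the primary model, and does not say which governs. An analyst who follows the 10% sentence alone obtains the biased result.

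Second, a full-model reference fits the text as well as a preceding-model one and keeps total drift below 10%. This also stands. The defect is that the choice is open, and a reader should not take the preceding-model reading as what the plan prescribes.

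Third, severity markers are correlated: Section 11.3 computes MELD from SCr, bilirubin and INR. Correlation makes the preceding-model rule mild, at −0.64 for correlation 0.3 and −0.61 with 96% coverage for 0.5. It does not help single screening, which stays at −0.75 for correlation 0.3.

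Fourth, other safeguards exist. Controls come from the study sites, must have met the same eligibility criteria, and baseline SCr is adjusted for outside the removal rule. The comparison with controls is listed as a secondary endpoint in Sections 5.1 and 13.2. These points limit the consequences, but they do not replace adjustment for the remaining imbalances, and Section 15.1 itself places the terlipressin association under the primary analysis.

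Finally, change-in-estimate selection starting from a full model is a recognised method. That is so, but it needs a stated reference and limit to be reproducible.

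**Conclusion.** The point holds in a limited form. Section 15.1 permits readings under which several confounders, each worth less than 10%, are all removed and a substantial part of their joint bias returns to the non-randomised comparison. In the assumed case of eight independent confounders, the estimate moves from −0.60 to about −0.77 mg/dL and 95% interval coverage falls to about 65%. Other permitted readings do little harm, and the plan does not choose among them.

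Two stronger conclusions are tempting. A reader might infer that most of the confounding returns as a rule. The documents do not support this: at the plan's 0.46 with SD 1.0, the preceding-model rule returned half or less in every scenario tried, and larger shares needed a larger effect relative to noise, a much larger sample, or single screening of correlated confounders. A reader might also infer that the rule exaggerates terlipressin's benefit. The documents give no imbalance data, and with the opposite imbalance the same rule understates the benefit.

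The number, strength, imbalance, correlation and direction of the confounders are all assumptions. What rests on the text alone is the missing reference model, the missing cumulative limit and the unstated precedence between the two rules.

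**What to change.** Make the primary comparison model a fixed, named set of pre-treatment covariates that the study already collects, kept whatever the data show. Candidates are enrollment SCr, bilirubin, INR, ACLF grade, age, transplant eligibility and alcoholic hepatitis. If MELD is used, it should replace its components rather than join them. With about 200 patients, 8 to 12 terms are affordable. Availability in the retrospective charts should be confirmed before the list is fixed. Report the 10% and AIC procedures as sensitivity analyses.

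If data-driven removal is kept, the minimum wording is that every reduced model is compared with the full-model coefficient, that the total change from the full model may not exceed 10%, and that this rule, not AIC, determines the primary model.

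The cost is a change of SAP wording and slightly wider intervals from keeping weak covariates. No new data collection is needed.
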